4.7.2. Additional Safety Assessments

Electrocardiograms

Electrocardiogram (ECG) will be summarized by visit and by treatment arm. A summary of change from baseline (by visit) and the corresponding AEs will also be provided.

Vital Signs

All vital signs (e.g., temperature, blood pressure, pulse rate, height, weight, heart rate) will be summarized by visit and by treatment arm. Treatment emergent abnormal changes in vital signs will also be summarized by treatment arm.

4.8. Other Analyses

4.8.1. Participant Characteristics

Demographics and baseline disease characteristics will be summarized by treatment arm.

Disease characteristics will include the following:

- Initial pathological diagnosis
- Disease stage (Stage IIA, Stage IIB, etc.)
- Histopathological diagnosis grade (G1, G2, etc.)
- Baseline Eastern Cooperative Oncology Group (ECOG) performance status (PS)
- Site of disease (liver, lung, etc.)
- Number of sites involved (1, 2, or 3+)
- Measurable disease at baseline (yes versus no)
- Endocrine resistance (primary versus secondary)

- Progesterone receptor status (positive versus negative)
- Nature of disease (visceral metastases, bone only metastases, or other)
- HER2 status (low versus negative)
- Prior CDK4/6 inhibitor (yes versus no)
 - If yes, setting (adjuvant versus metastatic)
 - If yes and received prior CDK4/6 inhibitor in the metastatic setting, length of the prior CDK4/6 inhibitor (≥ 12 months versus <12 months)
- Type of prior CDK4/6 inhibitor (e.g., palbociclib, ribociclib, abemaciclib, dalpiciclib)
- Prior therapy history
- ESR1 mutation status

Nature of disease, number of sites involved will be derived from the location codes of the targe and non-target lesions. All patients with at least 1 lesion on the baseline target lesion form will be considered as having measurable disease at baseline. Primary endocrine resistance is defined as relapse during the first 2 years of adjuvant endocrine therapy (ET), or progressive disease within the first 6 months of first-line ET for advanced/metastatic breast cancer. Secondary endocrine resistance is defined as relapse while on adjuvant ET but after the first 2 years or relapse within 12 months of completing adjuvant ET, or progressive disease 6 months after initiating ET for advanced/metastatic breast cancer.

4.8.2. Historical Illnesses/Preexisting Conditions

Historical illnesses and preexisting conditions (using MedDRA Preferred Terms) will be summarized by treatment arm.

4.8.3. **Prior Therapy**

Prior radiotherapy, surgery, and systemic therapy will be summarized by treatment arm. Prior radiotherapy and surgery will be categorized by reason for regimen. Prior systemic therapies will be categorized by type of regimen (endocrine therapy, chemotherapy, etc.) and reason for regimen (neoadjuvant, adjuvant, locally advanced, or metastatic). Frequency of each specific therapy will be tabulated within each type of therapy and per reason for regimen.

4.8.4. Concomitant Therapy

A summary of preferred names of concomitant medications by treatment arm by decreasing frequency will be reported.

4.8.5. **Post-Study Treatment Therapy**

The numbers and percentages of participants receiving poststudy anticancer therapies will be provided by type of therapy (surgery, radiotherapy, or systemic therapy), and by drug class and/or name, overall and by line of therapy.

4.8.6. Treatment Compliance

Treatment compliance for imlunestrant, exemestane, or abemaciclib will be assessed through pill counts at each cycle. Compliance will be calculated as the ratio of total dose taken to the total assigned dose (minus any dose adjustments and doses omitted/withheld for medical or logistical reasons). A patient will be considered noncompliant if he or she takes <80% or >125% of the planned doses. Compliance information for exemestane will be collected via number of doses at each cycle.

Compliance for fulvestrant is assured as the drug will be administered at the investigator site.

4.8.7. **Duration of Stable Disease**

Duration of stable disease is defined as the time from randomization to the date of objective progression of disease or death from any cause in the absence of disease progression. Participants will be censored using the same scheme as the main scheme for PFS.

4.8.8. Change in Tumor Size

Percent change in tumor size, defined as (post-baseline sum of target lesion measurementsbaseline sum of target lesion measurements)/baseline sum of measurements, will be summarized by cycle and by treatment arm. Mean percent change in tumor size will also be plotted by treatment arm. Repeated measures analysis may also be performed. Best percent change in tumor size is defined as the maximum post-baseline reduction (minimum percent change). The best percent change from baseline (per investigator assessment) will be presented per patient in a waterfall plot. The analysis of change in tumor size will be conducted in the ORR evaluable population.

4.8.9. Time to Response

Time to response (TTR) is defined as the time from the date of randomization to the date measurement criteria for CR or PR (whichever is first recorded) are first met. TTR will be summarized for each treatment arm. The analysis of TTR will be based on the participants who achieve an objective response (CR or PR).

4.8.10. Follow-up Time

Follow-up time is defined as the time from the date of randomization until death from any cause or last date the patient is known to be alive and under follow-up. Median follow-up time will be estimated using Kaplan-Meier estimation of potential follow-up ("reverse Kaplan-Meier") (Schemper and Smith 1996). The inverse of the censoring rules for the OS will be used (i.e., considering all censoring times for OS as event times (times when the patient is known to be still alive and under follow-up) and censoring patients who had OS events at the date of death.

4.8.11. Medical Resource Utilization

Frequency counts of hospitalizations, emergency room visits, radiation, surgery, transfusion, and analgesic use will be summarized descriptively for each arm.

Duration of hospital stays and average number of emergency room visits will be reported by treatment arm.

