Adverse Event Collection/ CTCAE Grading		Х	Х		Х	Х	Х	Х	Section 8.3	 Collect continuously at every visit and throughout the study CTCAE Version 5.0 For long-term follow-up: all SAEs regardless of relationship to study treatment and adverse events possibly related to study treatment will be collected All adverse events possibly related to study drugs or protocol procedures should be followed until they resolve, are no longer considered to be possibly related, become stable or return to baseline, the patient starts a new therapy, the patient expires, or the patient becomes lost to follow-up. The frequency of evaluation is determined according to the judgment of the investigator
Concomitant Medications		Х	x		Х	х	Х		Section 6.5	 At baseline, record prior and concurrent medications Record all pre-medications, supportive care, and concomitant medication continuously at every visit and throughout study
Lab/Diagnostic Tests	Coagulation	Х							Section 10.4 Appendix 4	 Perform at baseline and as clinically indicated Local testing

	Study Period	Baseline	Stu	Study Treatment (Cycle =28 day				ontinuation ow-Up		
	Cycle	Screening	1 a	nd 2	3	4 and Beyond (if Applicable)	Short-Term Follow-Up ^a	Long-Term Follow-Up ^a		
	Visit	0	1,3	2, 4	5	6 and Beyond (if Applicable)	801	802–8XX		
	Relative Day within a Cycle	≤28	Day 1	Day 15° (± 3)	Day 1 (± 3)	Day 1 (± 3)	Day 30 (± 7)	(± 14)		
Procedure Category	Procedure								Protocol Reference	Instructions
	Hematology	Х	Х	х	X	X	Х		Section 10.4 Appendix 4	 Assessments may be performed up to 3 days prior to Day 1 of each cycle Local testing Cycles 1 and 2 Day 15 hematology required for Arms A, C only
	Clinical chemistry	Х	х	x	Х	х	Х		Section 10.4 Appendix 4	 Assessments may be performed up to 3 days prior to Day 1 of each cycle Central testing Cycles 1 and 2 Day 15 clinical chemistry required for Arms A, C only
	FSH and estradiol levels	x				х	Х		See Section 5.1 and Section 10.4	 For Screening: local FSH/E2 testing for women <60 years when needed to confirm post-menopausal status For On study: local estradiol every 3 cycles, starting on Day 1 of Cycle 4 and again at STFU visit, for women whose postmenopausal status is due to GnRH agonist treatment
	Pregnancy test	Х					Х		Section 10.7 Appendix 7	 Local testing For Screening: serum pregnancy test required for women of child-bearing potential For on Study: per local regulations and/or institutional guidelines For Short-Term Follow-Up: local testing for women of child bearing potential

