Health Outcomes	Hospitalization and ED visits	Х			Х		Х		Section 8.9.9	
	SRE assessment	х			Х		х		Sections 8.9.9 & 9.4.7.1	
	Imlunestrant		PO (QD on Days 1 c	through 28 ycle	8 of every			Section 6.1	• See Section 6.1 for administration instructions
Study Drug	Fulvestrant			IM Days 1 and 15 (±3 days) of Cycle 1, then Day 1 (±3 days) of Cycle 2 and beyond					Section 6.1	 Administer per approved label See Section 6.1 for administration instructions
Administration	Exemestane		PO QD on Days 1 through 28 of every cycle					Section 6.1	 Administered per approved label See Section 6.1 for administration instructions 	
	Abemaciclib		PO BID	PO BID on Days 1 through 28 of every cycle					Section 6.1	• See Section 6.1 for administration instructions

Abbreviations: BID = twice daily; BIRC = blinded independent review committee; C = cycle; CT = computed tomography; CTCAE = Common Terminology Criteria for Adverse Events; D = day; ECG = electrocardiogram; ECOG = Eastern Cooperative Oncology Group; ED = emergency department; FSH = follicular stimulating hormone; IM = intramuscular; MRI = magnetic resonance imaging; PE = physical exam; PK = pharmacokinetics; PO = orally; PRO = patient-

reported outcome; PS = performance status; QD = once daily; RECIST = Response Evaluation Criteria in Solid Tumors; SAEs = serious adverse events; SRE = skeletal-related event: STFU = short-term follow-up.

- ^a Short-term follow-up period begins the day after the patient and the investigator agree that the patient will no longer continue study treatment and lasts approximately 30 days; the associated study procedures should be performed once at the end of the short-term follow-up period (approximately 30 days after the last dose of study drug). Long-term follow-up period begins the day after the short-term follow-up visit is completed and continues until the patient's death or overall study completion; the associated study procedures are performed approximately every 12 weeks (± 14 days) for the duration of this period beginning 12 weeks after the short-term follow-up visit.

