8.9.9. Medical Resource Utilization

Medical resource utilization will be collected in the eCRF by the investigator and study site personnel for all patients throughout the study. Protocol-mandated procedures, tests, and encounters are excluded. The data collected will include hospitalization, emergency room visit, radiation, surgery, and analgesic use.

9. Statistical Considerations

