9.4.4. Patient-Reported Outcomes and Medical Resource Utilization

Time to sustained worsening of worst pain is defined from the randomization to the time of the first increase (≥ 2 points) in the weekly average of the worst pain score with confirmation in the next consecutive week. Time to sustained worsening of worst pain will be summarized for each arm by the Kaplan-Meier method and will be compared between the 2 arms using the stratified log-rank test.

Time to worsening of physical function is defined as the time from randomization to the first \geq 10-point decrease from baseline with confirmation at the next cycle. Time to worsening of physical function will be summarized for each arm by the Kaplan-Meier method, and the stratified log-rank test will be used to compare between the 2 arms.

For each participant with data from baseline and at least 1 post-baseline visit, the change from baseline at each time point, and maximum change from baseline score will be calculated for each scale of each instrument. The reason and number of missing and incomplete questionnaires and/or assessments by visit will be summarized for each instrument and arm.

Frequency counts of hospitalizations, emergency room visits, radiation, surgery, transfusion, and analgesic use will be summarized descriptively for each arm.

Full censoring rules for these endpoints will be described in the SAP. All the analyses will be conducted for each comparison (Arm A versus Arm B in the ITT and the *ESR1*-mutation detected populations and Arm C versus Arm A in the ITT population) per the prespecified analysis populations. Further analysis details will be described in the SAP.

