1.2. Study Design

In the protocol amendment (a), participants will be randomized 1:1:1 between 3 treatment arms (Arm A: Arm B: Arm C) and will be treated until disease progression or other discontinuation criteria are met (Protocol Section 7).

- Arm A: Imlunestrant 400 mg orally QD on Days 1 to 28 of a 28-day cycle
- Arm B: Investigator's Choice Endocrine Therapy
 - Exemestane 25 mg orally QD on Days 1 to 28 of a 28-day cycle OR

- Fulvestrant 500 mg intramuscularly on Days 1 and 15 of Cycle 1, then on Day 1 of Cycle 2 and beyond
- Arm C: Imlunestrant + Abemaciclib
 - Imlunestrant 400 mg orally QD on Days 1 to 28 of a 28-day cycle
 - Abemaciclib 150 mg orally BID on Days 1 to 28 of a 28-day cycle

Arm C was added to the study (amendment a) after first patient visit for Arms A and B. All arms will be closed at the same time. Randomization of participants will continue in Arms A and B (1:1) until amendment (a) is approved and implemented, at which point participants will be randomized 1:1:1 (A:B:C) until the target enrollment for arms A and B (a total number of approximately 640 participants) is reached.

Investigator's Choice Endocrine Therapy (fulvestrant or exemestane) must be selected prior to randomization. Participants will be randomized using the following stratification factors:

- previous treatment with any CDK4/6 inhibitor (yes versus no)
- presence of visceral metastases (yes versus no); visceral includes lung, liver, brain, pleural, and peritoneal involvement, and
- region (East Asia versus North America/Western Europe versus Others).

The primary study objectives are to

- compare the PFS of Arm A to Arm B in the ITT population
- compare the PFS of Arm A to Arm B in the ESR1-mutation detected population, and
- compare the PFS of Arm C to Arm A in the ITT population.

The schema of the study is shown below.

Note: *ESR1*-mutation status will be centrally determined in plasma by Guardant 360 ctDNA assay from a blood draw at baseline.

Abbreviations: AI = aromatase inhibitor; CDK = cyclin-dependent kinase; ctDNA = Circulating tumor DNA; ER+ = estrogen receptor positive; FPV = first patient visit; HER2- = human epidermal growth factor receptor 2 negative; mTOR = mammalian target of rapamycin; n = number of participants; PI3K = phosphoinositide 3-kinase; PO = orally; QD = once daily; R = randomization; SERD = selective estrogen receptor degrader.

2. Statistical Hypotheses

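### Resource-use counts are reported per arm with no denominator for time observed, and the protocol gives two different collection windows for them

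*SAP*

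**What the plan says.** **Analysis.** SAP 4.8.11 consists of two sentences. The first is "Frequency counts of hospitalizations, emergency room visits, radiation, surgery, transfusion, and analgesic use will be summarized descriptively for each arm"; the second is "Duration of hospital stays and average number of emergency room visits will be reported by treatment arm". Protocol 9.4.4 contains the same frequency-count plan. That section covers patient-reported outcomes and resource use together, and says "All the analyses will be conducted for each comparison", on the prespecified analysis populations. No test, ratio or difference is specified for resource use, and no person-time denominator appears.

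**Collection.** There are two statements.
- The Schedule of Activities (Protocol 1.3) has a row "Hospitalization and ED visits", marked at baseline, during study treatment and at short-term follow-up (Visit 801). The long-term follow-up cell is empty. Footnote a says the short-term period "begins the day after the patient and the investigator agree that the patient will no longer continue study treatment and lasts approximately 30 days".
- Protocol 8.9.9 says "Medical resource utilization will be collected in the eCRF by the investigator and study site personnel for all patients throughout the study".

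**Treatment duration.** According to SAP 1.2, patients "will be treated until disease progression or other discontinuation criteria are met".

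**The concern.** If the Schedule of Activities governs, the observation period for hospitalizations and emergency visits ends about a month after treatment stops. Most patients stop at progression, so the length of that period is itself affected by treatment. An arm with longer PFS then accumulates events over more months. Dividing by the number of patients, as an average per patient does, leaves this in place because it does not divide by time.

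The table would be laid out by arm in a randomized trial, and readers will compare the columns. A difference produced by unequal observation time could be read as a difference in how often patients need hospital care. Raw totals for Arm C versus Arm A have a second problem if all of Arm A is shown, because the planned arm sizes are 220 and 320.

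**Working it through.** **Inputs from SAP Section 5 (also Protocol 9.2).** Median PFS is 4.3 months in Arm B with hazard ratio 0.74 for A versus B. It is 5.8 months in Arm A with hazard ratio 0.70 for C versus A. In the ESR1-mutation subset it is 3.6 months in Arm B with hazard ratio 0.57. Survival is exponential.

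**The plan's own figures first.** No figure is stated for resource use. The PFS gains that drive time on treatment reproduce:
- A versus B: 4.3/0.74 = 5.81 months, a gain of 1.51 (stated: about 1.5).
- C versus A: 5.8/0.70 = 8.29 months, a gain of 2.49 (stated: about 2.5).
- ESR1-mutation subset: 3.6/0.57 = 6.32 months, a gain of 2.72 (stated: about 2.7).

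**Assumptions added.** The Schedule's window applies, with its on-treatment mark read as covering the whole treatment period. Treatment stops at progression, the follow-up tail is 1 month, and the event rate is constant and the same in every arm.

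**Mean months observed per patient.** With mean time on treatment μ = median/ln 2:
- No data cut: μ + 1.
- Observation cut L months after randomization: 1 + μ(1 − exp(−(L − 1)/μ)).

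μ is 6.20 (B) and 8.38 (A) for A versus B. It is 8.37 (A) and 11.95 (C) for C versus A, where A's median is taken as the stated 5.8.

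| Data cut | B | A | A/B | A | C | C/A |
|---|---|---|---|---|---|---|
| 12 months | 6.15 | 7.13 | 1.16 | 7.12 | 8.19 | 1.15 |
| 24 months | 7.05 | 8.84 | 1.25 | 8.83 | 11.21 | 1.27 |
| none | 7.20 | 9.38 | 1.30 | 9.37 | 12.95 | 1.38 |

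At equal rates, the ratio of expected events per patient equals the ratio of months observed, whatever the rate. The same calculation in the ESR1-mutation subset gives 7.39/5.57 = 1.33 at 12 months, 9.38/6.13 = 1.53 at 24 months and 10.11/6.19 = 1.63 with no cut.

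**Illustration in counts.** The documents give no event rate, so I assume 0.05 per patient-month in every arm, with no data cut:
- B versus A, 320 patients each: 320 × 0.05 × 7.20 = 115 against 320 × 0.05 × 9.38 = 150.
- A versus C, 220 patients each: 220 × 0.05 × 9.37 = 103 against 220 × 0.05 × 12.95 = 142.
- At 0.02 and 0.10 per patient-month, the B versus A counts are 46 against 60 and 230 against 300.

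**If counts mean patients rather than events.** The share with at least one event is 1 − exp(−λ)/(1 + λμ). At λ = 0.05 this is 27% (B) against 33% (A), and 33% (A) against 40% (C). The distortion is smaller but remains.

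**With a denominator.** Events divided by patient-months give an expected rate ratio of 1.00 in each comparison under the same assumptions.

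**The case against.** **The window is not settled.** The limit of about 30 days rests on an empty cell in one Schedule row, and Protocol 8.9.9 says otherwise. The blank looks deliberate, since the survival and adverse-event rows are marked in long-term follow-up, but the documents do not decide the matter. If 8.9.9 governs, observation continues past treatment, the effect shrinks, and what is left depends on survival follow-up. Some related information is collected later in any case: in long-term follow-up the adverse-event row covers "all SAEs regardless of relationship to study treatment", and post-study surgery and radiotherapy are summarized. Those are separate data streams from resource use. This objection stands, so the result is conditional on the window.

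**A reader might infer that the plan formally compares raw counts.** It does not. The output is descriptive, no test is specified, and resource use is not a listed primary, secondary or exploratory endpoint.

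**A reader might infer that the better arm must look worse.** That holds only in expectation at equal or nearly equal rates. If the longer-treated arm has a lower rate, the counts reverse once the reduction exceeds 1 − 1/ratio. That is about 23% (A versus B) and 28% (C versus A) with no cut, and about 14% and 13% with a 12-month cut.

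**A reader might infer a wrong health-economic conclusion.** The protocol ties economic evaluation to EQ-5D-5L (8.9.4). Neither 8.9.9 nor SAP 4.8.11 gives these counts that purpose.

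**Exposure is reported elsewhere.** SAP 4.7.1 gives cycles received and duration of therapy, so a reader could notice unequal exposure. That does not adjust the counts. The follow-up time in SAP 4.8.10 is based on overall survival and would be the wrong denominator under the Schedule's window.

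**Not every output is affected.** Hospital-stay duration may mean length per stay, which need not grow with time observed.

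**Conclusion.** The point holds as a small improvement to a descriptive table. Two things are established from the text: resource use has no denominator for time observed, and Protocol 8.9.9 and the Schedule of Activities give different collection periods. The size is conditional. If the Schedule's window applies, treatment stops at progression and the design PFS assumptions hold, equal rates give an expected excess per patient of about 16-30% for A over B and 15-38% for C over A. The lower ends correspond to a 12-month cut and the upper ends to no cut. Stopping early for toxicity, or continuing past progression with sponsor agreement, would change these figures. Alpha, power and the primary conclusions are untouched, and the documents do not support a claim that the table will mislead in a fixed direction.

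**What to change.** - **Window.** State one collection period and use it in both Protocol 8.9.9 and the Schedule of Activities. The sponsor must say which is intended.
- **Rates.** In SAP 4.8.11, keep the counts and say whether they are events or patients. For the countable items (hospitalizations, hospital days, emergency visits, and radiation, surgery and transfusion episodes), add events per patient-month at risk by arm. Time at risk ends at the close of the stated collection window, death or data cutoff, whichever is first.
- **Population.** Say in SAP 4.8.11 that C versus A uses the concurrently randomized patients. Protocol 9.4.4 already implies this.
- **Analgesics.** Report analgesic use as the proportion of patients, with observation time shown alongside, because it is not naturally an event count.
- **Source of transfusion data.** The SAP counts transfusions, but the list of collected data in Protocol 8.9.9 does not name them. Name the source in the same edit.

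The cost is slightly more analysis work and a small wording correction to the protocol or the Schedule. Under the Schedule's window the dates needed (randomization or first dose, Visit 801, death, cutoff) are ordinary trial data.
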